8.7.3 Secondary Efficacy Analysis

Appropriate descriptive statistics will be computed for all secondary efficacy parameters.

The percent change from Baseline to Week 12 in inflammatory lesion counts and the absolute change from Baseline in inflammatory lesion counts at Week 8 and Week 4 will be analyzed using the same ANCOVA method described for the primary endpoint.

The proportion of subjects who are dichotomized to success (“clear” or “almost clear”) at Week 8 and Week 4 will be analyzed using the same logistic analysis method described for the co-primary endpoint.

A stepwise process will be conducted for testing the secondary efficacy endpoints in order to control for multiplicity, refer to Section 8.1.8.

The secondary efficacy analysis will be presented on only the ITT population.

8.7.4 Supportive Efficacy Analysis

Appropriate descriptive statistics will be computed for all supportive efficacy parameters.

In addition, the mean change comparison in PAPSS item 1 (burning), item 2 (itching), item 3 (redness) and item 4 (bumps) from Baseline to Week 12 will be analyzed using an analysis of variance (ANOVA) with factors of treatment, analysis center, and the respective Baseline score. Missing values will not be imputed.

A set of cumulative distribution function curves will be generated to allow for the evaluation of within-person change by treatment group. Specifically, 5 plots will be generated showing the change from Baseline to Week 12 (and/or other, earlier time points if so desired) by the cumulative percent of subjects for each of the treatment arms (change on the x-axis will be expressed as absolute change) on:

- PAPSS total scale scores

- The total scale score is the sum of PAPSS items 1 through 4.
 - PAPSS item 1 (burning) scores
 - PAPSS item 2 (itching) scores
 - PAPSS item 3 (redness) scores
 - PAPSS item 4 (bumps) scores

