## 5.2. Study Flow Chart

Procedures	Visit 1 	Visit 2 	Visit 3 	Visit 4 	Visit 5 	Visit 6  (EOT  / EOS  )
Name of Visit	Screening -35 – 0	Baseline Day 1	Week 2 Day 15	Week 4 Day 29	Week 8 Day 57	Week 12 Day 85
Visit window			± 3 days	± 3 days	± 3 days	± 4 days
Informed Consent	X					
Demographics	X					
Medical History/Previous Therapies	X	X				
Brief Physical Examination		X				X
Inclusion/Exclusion Criteria	X	X				
Urine Pregnancy Test 	X	X		X	X	X
IGA	X	X	X	X	X	X
Inflammatory Lesion Counts	X	X	X	X	X	X
Assessment of Eligibility		X				
Rosacea Erythema Assessment		X	X	X	X	X
Telangiectasia Assessment		X	X	X	X	X
Randomization		X				
Cutaneous Safety Assessment and Local Tolerability Assessments		X	X	X	X	X
Administer/ Review Patient Instructions		X	X	X	X	
Weigh Study Product		X		X	X	X
Study Product Dispensed		X 		X	X	
Provide Cleanser and Moisturizer/Sunscreen 		X				
Diary Card dispensed		X		X	X	
Study Product Collected				X	X	X
Diary Card collected				X	X	X
Patient Compliance Reviewed (Diary)			X	X	X	X
Concomitant Therapy and Medication History Reviewed	X	X	X	X	X	X
Adverse Events	X 	X	X	X	X	X
Photography (select site(s))		X	X	X	X	X
Complete PAPSS, PAPI and PGI-S 		X	X	X	X	X
Complete PGI-C, PGI-TS and PGI-SE 			X	X	X	X
Complete RosaQoL 		X				X

 If no washout is needed, Visits 1 and 2 may occur on the same day. If a washout is needed, Visit 2 must occur within one month 35 days of Visit 1.

 All visit dates are in reference to Baseline, e.g., Visit 5 occurs 8 weeks ± 3 days after Baseline Visit.

 All Week 12 procedures should be completed for Patients who terminate early.

 EOT – end of treatment

 EOS – end of study

 All women of childbearing potential

 Dispense one pump of test material at the Baseline Visit and dispense additional pump at Visit 4 and 5.

 Or study approved cleanser and moisturizer

 Adverse events after ICF is signed will be collected.

 PAPSS is Patient Assessment of Papulopustular rosacea Signs and Symptoms; PAPI is Patient Assessment of Papulopustular rosacea Impacts; PGI-S is Patient Global Impression of Symptom Severity. Questionnaires will be completed prior to PI assessment.

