## 7. INTRODUCTION AND BACKGROUND

S5G4T-1 is an innovative topical formulation containing 5% encapsulated benzoyl peroxide (E-BPO) that Sol-Gel is developing for the treatment of rosacea. If approved, S5G4T-1 will be the first product containing E-BPO for the treatment of rosacea. Sol-Gel believes S5G4T-1 has the potential to be as tolerable as, and more effective than, currently marketed rosacea drugs.

Rosacea is a chronic and recurrent inflammatory dermatological disorder of unknown etiology. The disease is common, especially in fair-skinned people of Celtic and northern European heritage. The onset of the disorder is usually between the ages of 30 and 50. Early stages of the disease affect women more often than men at a ratio of 3 to 1 (Jansen and Plewig 1997 and McDonnell and Tomecki 2000). Rosacea usually starts as flushing and subtle redness on the cheeks, nose, chin or forehead. Alcohol, hot drinks, spicy foods, stress, sunlight and extreme heat or cold can trigger the onset of this disease. If left untreated, rosacea can slowly worsen over time. As the condition progresses, patients experience inflammatory lesions (papules and pustules), vivid erythema and telangiectasia. Patients may develop furuncles, cystic nodules, granulomas and tissue hypertrophy, sometimes leading to rhinophyma.

The first report on the treatment of rosacea with benzoyl peroxide as a single agent was described by in Montes *et al.* in 1983. In this limited study, 5% benzoyl peroxide, after 5 to 8 weeks of treatment, demonstrated superiority compared to control with respect to papules, pustules and erythema but not telangiectasia. The formulation was a basic formulation with benzoyl peroxide dissolved and delivered in acetone. Irritation and burning was reported in both groups, most likely due to the well-known effects of benzoyl peroxide.

More recently, Breneman *et al.* 2004 published the results of a study in collaboration with J. Leyden. This study was a double-blind, vehicle-controlled study, using a combination gel product of 5% benzoyl peroxide and 1% clindamycin to treat patients having moderate to severe rosacea. The most dramatic effect of the benzoyl peroxide/clindamycin treatment was on the reduction of papules and pustules. Side effects included the well-known effects of benzoyl peroxide, burning and itching.

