#### 19.4.4. Supportive Efficacy Analyses

Appropriate descriptive statistics will be computed for all Supportive Efficacy parameters. Additionally, inferential testing for the following endpoints will use an ANOVA with factors of treatment, analysis center and the respective Baseline score. The overall Type I error will be controlled by the Benjamini-Hochberg method. Missing values will not be imputed.

- Mean change comparison in PAPSS item 1 (burning) between groups from Baseline to Week 12
- Mean change comparison in PAPSS item 2 (itching) between groups from Baseline to Week 12
- Mean change comparison in PAPSS item 3 (redness) between groups from Baseline to Week 12
- Mean change comparison in PAPSS item 4 (bumps) between groups from Baseline to Week 12

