6. STUDY DESIGN

6.1 Overall Study Design

This study will be a randomized, double-blind, multicenter, parallel group, active- and vehicle-controlled pivotal study of the efficacy and safety of S5G4T-1 and its vehicle for the treatment of papulopustular rosacea for 12 weeks. Approximately 350 patients with moderate to severe rosacea (rated 3 or 4 on the 5-point IGA scale) will be enrolled at up to 28 sites. Patients in this randomized, double-blind, vehicle-controlled, parallel-group multi-center study will be randomly assigned in a 2:1 ratio to S5G4T-1 or vehicle, respectively. Subjects with severe rosacea who are appropriate for systemic treatment need to be counseled regarding their treatment options by the Principal Investigator.

Patients will receive once daily treatment with S5G4T-1 or vehicle cream for 12 weeks. After the screening period, qualified patients will be randomly assigned at the Baseline visit and treated for 12 weeks. Efficacy assessments will include facial inflammatory lesion counts and IGA assessment ranging from 0 (clear) to 4 (severe). Investigators will be provided with instructions for lesion counts to ensure consistency of procedure. Patient reported outcomes (PRO) will be assessed with the PAPSS (Patient Assessment of Papulopustular Rosacea Signs and Symptoms), PAPI (Patient Assessment of Papulopustular rosacea Impacts), and PGI-S (Patient Global Impression of Symptom Severity) that will be administered at Baseline, Weeks 2, 4, 8, and 12, or at early termination. In addition, the PGI-C (Patient Global Impression of Change), PGI-TS (Patient Global Impression of Treatments Satisfaction), and PGI-SE (Patient Global Impression of Treatments Side Effects) will be administered at Weeks 2, 4, 8, and 12, or at early termination [FDA Guidance 2009]. Safety will be assessed at all visits and will include monitoring local and systemic adverse events (AEs); the Investigator Cutaneous Safety Assessment rating of

erythema, dryness and scaling, and the Local Tolerability Assessments rating of itching and burning/stinging on a scale ranging from 0 (none) to 3 (severe).

Patients will return to centers for IGA, lesion counts, PRO questionnaire, Investigator Cutaneous Safety Assessment, and Local Tolerability Assessments at Weeks 2, 4, 8 and 12. AEs and concomitant medications will be assessed throughout the treatment period. A urine pregnancy test is required at Visit 1, 2, 4, 5, and 6 for all females of child-bearing potential.

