8.1.3 Visit Windowing

Data will be summarized based on nominal visit indications with the exception of data captured at early termination and unscheduled visits. Data from early termination and unscheduled visits will be summarized based on mapped visit values. The analysis windows for early termination and unscheduled visits are presented in the following table.

Analysis Windows for Efficacy and Safety Assessments

Scheduled Visit	Target Study Day	Window (Days)
Week 2	15	8 to 21
Week 4	29	22 to 42
Week 8	57	43 to 70
Week 12	85	71 to 98

Data collected at early termination and unscheduled visits prior to study day 8 will not be analyzed, with the exception of those identified as Baseline values. Data collected at early termination and unscheduled visits after study day 98 will not be included in analyses.

The definition for the study day included in each study window is defined as below:

Study Day prior to Day 1 = Visit Date – Day 1 Date

Study Day on or after Day 1 = Visit Date – Day 1 Date + 1

If an assessment's mapped visit is a visit at which the subject has data from a scheduled visit present, or if no analyses are planned for the assessment at the mapped visit, the data collected at the early termination or unscheduled visit will not be included in analyses.

In the event of multiple values from unscheduled or early termination assessments within an analysis window, the value closest to the scheduled visit target study day will be used for analyses. If two values tie as closest to the time point (for example, one value is before and the other value is after the time point), then the later value will be selected.

Data collected at all visits will be included in the data listings with visit presented as reported by the site.

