LSSD ^a	xx.xx	xx.xx	
PAPSS Redness – Absolute Change from Baseline to Week 12			
LSMean ^a	xx.x	xx.x	x.xxx ^a
LSSD ^a	xx.xx	xx.xx	
PAPSS Bumps – Absolute Change from Baseline to Week 12			
LSMean ^a	xx.x	xx.x	x.xxx ^a
LSSD ^a	xx.xx	xx.xx	

^a Least squares means, standard deviations and treatment p-value from an analysis of variance with factors of treatment, analysis center, and the respective Baseline score. Negative least squares means values represent decrease from Baseline.

Note: No imputation of missing values. To control family-wise type I error rate at 5%, the Benjamini-Hochberg procedure (Hochberg and Bejamini adaptive step-down Bonferroni method) was utilized, and each p-value with an (*) is to be considered statistically significant.

SOURCE: USERNAME\SPONSOR\PROJECT\JOBNAME (DATE, TIME)

Table 14.2.8.1: Summary of Patient Assessment of Papulopustular Rosacea Signs and Symptoms (PAPSS) at Each Evaluation
(Intent-to-Treat Population)
(Page 1 of 15)

Total Scale Scores	E-BPO 5% Cream (N=xxx)	Vehicle Cream (N=xxx)
Baseline		
n	xx	xx
Mean	xx.x	xx.x
SD	xx.xx	xx.xx
Median	xx.x	xx.x
Min. to Max.	xx to xx	xx to xx
Week 2		
n	xx	xx
Mean	xx.x	xx.x
SD	xx.xx	xx.xx
Median	xx.x	xx.x
Min. to Max.	xx to xx	xx to xx
Change from Baseline		
n	xx	xx
Mean	xx.x	xx.x
SD	xx.xx	xx.xx
Median	xx.x	xx.x
Min. to Max.	xx to xx	xx to xx

Note: No imputation of missing values.

Total scale score is the sum of all PAPSS items.

SOURCE: USERNAME/SPONSOR/PROJECTJOBNAME (DATE,TIME)

Table 14.2.8.1: Summary of Patient Assessment of Papulopustular Rosacea Signs and Symptoms (PAPSS) at Each Evaluation
(Intent-to-Treat Population)
(Page 2 of 15)

Total Scale Scores	E-BPO 5% Cream (N=xxx)	Vehicle Cream (N=xxx)
Week 4		
n	xx	xx
Mean	xx.x	xx.x
SD	xx.xx	xx.xx
Median	xx.x	xx.x
Min. to Max.	xx to xx	xx to xx
Change from Baseline		
n	xx	xx
Mean	xx.x	xx.x
SD	xx.xx	xx.xx
Median	xx.x	xx.x
Min. to Max.	xx to xx	xx to xx
Week 8		
n	xx	xx
Mean	xx.x	xx.x
SD	xx.xx	xx.xx
Median	xx.x	xx.x
Min. to Max.	xx to xx	xx to xx
Change from Baseline		
n	xx	xx
Mean	xx.x	xx.x
SD	xx.xx	xx.xx
Median	xx.x	xx.x
Min. to Max.	xx to xx	xx to xx

Note: No imputation of missing values.

Total scale score is the sum of all PAPSS items.

SOURCE: USERNAME\SPONSOR\PROJECT\JOBNAME (DATE,TIME)

Table 14.2.8.1: Summary of Patient Assessment of Papulopustular Rosacea Signs and Symptoms (PAPSS) at Each Evaluation
(Intent-to-Treat Population)
(Page 3 of 15)

Total Scale Scores	E-BPO 5% Cream (N=xxx)	Vehicle Cream (N=xxx)

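### The Week 12 PAPSS item tests leave out most patients who stop before Day 71, so burning and itching may be biased in a direction the documents cannot settle

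*SAP*

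**What the plan says.** SAP 8.7.4 tests burning, itching, redness and bumps as change from Baseline to Week 12, in an ANOVA "with factors of treatment, analysis center, and the respective Baseline score. Missing values will not be imputed". Protocol 19.4.4 lists the same Week 12 comparisons, starting with "Mean change comparison in PAPSS item 1 (burning) between groups from Baseline to Week 12", under the same rule: "Missing values will not be imputed". The planned display, SAP Table 14.2.7.1 (ITT population), carries a note that begins "Note: No imputation of missing values. To control family-wise type I error rate at 5" percent, so the p-values are presented as adjusted for multiplicity. The PAPSS cumulative distribution figures are also drawn without imputation.

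Scores do exist for patients who leave. SAP 6.1 describes PAPSS as one of the instruments "that will be administered at Baseline, Weeks 2, 4, 8, and 12, or at early termination", and a footnote to the Protocol 5.2 flow chart adds "All Week 12 procedures should be completed for Patients who terminate early". That footnote does not turn an early-termination score into a Week 12 score. SAP 8.1.3 states "Data from early termination and unscheduled visits will be summarized based on mapped visit values", and its table counts a value as Week 12 only on Days 71 to 98. Days 8 to 70 map to Week 2, 4 or 8. Early-termination values before Day 8 are not analyzed, and a mapped value is dropped if the patient has scheduled-visit data for that visit. Protocol 13.14 ends the early-termination visit with discharge and describes no later Day 85 assessment.

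The treatment-failure value in SAP 8.1.5 is defined for lesion count and IGA only. The sensitivity analyses in SAP 8.7.2 cover the co-primary endpoints only. None is planned for PAPSS.

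**The concern.** Burning and itching are symptoms that can themselves lead a patient to stop. Of an earlier combination gel containing benzoyl peroxide, Protocol 7 says "Side effects included the well-known effects of benzoyl peroxide, burning and itching". SAP 4 reports moderate stinging, burning and pruritus in a few Phase 2 patients, and Protocol 17.7 has patients with a severe related adverse event discontinued. Missing Week 12 scores on these two items may therefore depend on the value that would have been recorded.

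For lesion count and IGA the SAP takes such exits seriously, with multiple imputation, a failure value and two sensitivity analyses each. For PAPSS it uses observed cases alone, yet presents error-controlled p-values. Multiplicity control does not correct for selective loss. At stake is whether a nominally significant result for burning or itching describes all patients in the ITT population or only those who stayed.

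**Working it through.** **What the plan states.** There is no sample size, power, standard deviation or dropout rate for PAPSS, so no PAPSS figure can be reproduced. The co-primary sample sizes do reproduce. IGA success of 53.3% against 20.0% at 2:1 and 95% power gives 86 and 43 with continuity correction. For lesion count, the SE is √(6.70²/200 + 17.24²/100) = 1.79, and the power is 96.0% to 96.3% against the stated 95%. Only the planned enrollment of 234 and 117 is carried forward.

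**Who leaves the test.** Setting SAP 8.7.4 beside SAP 8.1.3:

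- Stop with an early-termination visit on Days 71 to 98: the score counts as Week 12 and the patient stays in.
- Stop with an early-termination visit on Days 8 to 70: the score goes to Week 2, 4 or 8, or is dropped if that visit already has scheduled data; the patient is out of the Week 12 test.
- Stop before Day 8: the early-termination score is not analyzed; the patient is out.
- Stop applying the product but attend Week 12: the patient stays in.

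**Size, under assumptions that are not in the documents.** Let d be the share of an arm lost for irritation, and g the number of points by which their change is worse than that of patients kept. The arm's full mean is then the observed mean plus d × g. With the same g in both arms:

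missed difference (E-BPO minus vehicle) = (d_E-BPO − d_vehicle) × g

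| E-BPO lost | Vehicle lost | g = 2 | g = 4 | g = 6 |
|---|---|---|---|---|
| 2% | 0% | 0.04 | 0.08 | 0.12 |
| 3% | 1% | 0.04 | 0.08 | 0.12 |
| 5% | 1% | 0.08 | 0.16 | 0.24 |
| 5% | 2% | 0.06 | 0.12 | 0.18 |
| 10% | 2% | 0.16 | 0.32 | 0.48 |
| 5% | 5% | 0 | 0 | 0 |

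Positive values are a disadvantage of E-BPO that the test does not see. The losses correspond to about 5 to 23 of 234 patients on E-BPO.

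**Scale.** SE = SD × √(1/234 + 1/117) = SD × 0.1132. For an assumed SD of 2.0, 2.5 and 3.0 the SE is 0.226, 0.283 and 0.340, and 1.96 × SE is 0.44, 0.56 and 0.67 points. A middle case (5% against 2%, g = 4) misses 0.12 points, or 0.12/0.283 = 0.42 SE at SD 2.5.

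**The sign can reverse.** If the arms lose patients for different reasons, the missed difference is d_E-BPO × g_E-BPO − d_vehicle × g_vehicle. Suppose 2% leave E-BPO for irritation with g = 4, and 5% leave vehicle for lack of effect with g = 2. The result is 0.08 − 0.10 = −0.02, a slight lean toward vehicle.

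**The case against.** A reader might infer that the tests must favor E-BPO. The documents do not support this. The Protocol 7 sentence on burning and itching concerns a benzoyl peroxide/clindamycin gel, a different product. SAP 4 describes tolerability of the encapsulated product in Phase 2 as good. No dropout rate by arm is given, and lack of efficacy is a listed reason for withdrawal that would act against vehicle. The PAPSS items, as worded in Table 14.2.8.1, ask about symptoms due to the rosacea, so burning that a patient blames on the cream may be scored only in part. That makes any assumed gap uncertain. All of this stands.

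A reader might also turn the shift into an inflated false-positive rate. With an excess loss of 2% to 5%, a gap of 3 to 4.5 points and an SD of 2 to 3, k = bias/SE runs from 0.06/0.340 = 0.18 to 0.225/0.226 = 0.99. Then Φ(−1.96 + k) + Φ(−1.96 − k) runs from 5.4% to 17%, and is 7.6% at 3%, 4.5 points and SD 2.5. The arithmetic is right, but every input is assumed. The upper figure needs all three worst values at once, and the calculation supposes a true difference of exactly zero with no offsetting loss on vehicle. It cannot be offered as a property of this trial.

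Nor are irritation exits hidden. Local Tolerability scores are tabulated by arm and visit, reactions that lead to discontinuation become adverse events, discontinuations for adverse events are counted by arm, and PAPSS is summarized at Weeks 2, 4 and 8. This limits the concern to the inferential test, but none of these displays changes its Week 12 p-value.

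**Conclusion.** The point holds in a limited form. The Week 12 PAPSS tests normally exclude patients who stop before Day 71, although earlier scores for most of them should exist, and no sensitivity analysis examines the effect. The bias is toward E-BPO if irritation exits predominate there, and the other way if vehicle exits for lack of effect predominate. Neither direction nor size can be settled from the documents. Illustratively, the missed difference is 0 to about 0.5 points, resting wholly on the assumed losses and gaps.

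PAPSS is a supportive endpoint outside the co-primary and stepwise secondary testing, so this is a minor improvement and no co-primary or secondary conclusion depends on it. It is worth making because the data are already collected and SAP 8.7.2 already plans a model of the same structure for lesion count.

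**What to change.** In SAP 8.7.4, analyze each PAPSS item with a repeated-measures model over Weeks 2, 4, 8 and 12, with treatment, analysis center, visit, treatment-by-visit and Baseline score. Include early-termination scores as mapped by SAP 8.1.3, and test the Week 12 contrast. Keep the observed-case ANOVA as a sensitivity analysis.

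The model assumes that missingness depends only on observed data, and it does not recover early-termination scores that SAP 8.1.3 discards. So add a second sensitivity analysis that assigns an unfavorable value, such as the early-termination score or no change from Baseline, to patients who stop for a related adverse event or for lack of effect. Apply it alike to both groups of leavers and to both arms. Carrying scores forward only for related-adverse-event leavers, inside the main test, would be an asymmetric single imputation and could build in the opposite bias.

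Report the number excluded at Week 12 by arm and reason, amend Table 14.2.7.1, and record the departure from Protocol 19.4.4 in SAP 10.

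The cost is SAP wording, one extra model per item plus the added sensitivity analysis, and possibly less favorable burning and itching results. No new data are needed.

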8.7.5 Exploratory Endpoint Analysis

The mean change in RosaQoL subscale scores from Baseline to Week 12 will be summarized using descriptive statistics.

The subscores for the RosaQoL are computed as follows:

Total Score: the unweighted mean of all RosaQoL questions

Symptom subscale score: the unweighted mean of the following symptom questions

My rosacea burns or stings (item #2)

My rosacea is irritated (item #6)

My rosacea makes my skin sensitive (item #9)

My skin feels bumpy (uneven, not smooth, irregular) (item #16)

My skin flushes (item #17)

My skin gets irritated easily (cosmetics, aftershaves, cleansers) (item #18)

My eyes bother me (feels dry or gritty) (item #19)

Functional subscale score: the unweighted mean of the following functional questions

I try to cover up my rosacea (with make-up) (item #13)

I avoid certain foods or drinks because of my rosacea (item #15)

I avoid certain environments (heat, humidity, cold) because of my rosacea (item #21)

Emotion subscale score: the unweighted mean of the following emotion questions

I worry that my rosacea may be serious (item #1)

I worry about getting scars from my rosacea (item #3)

I worry that my rosacea may get worse (item #4)

I worry about side effects from rosacea medications (item #5)

I am embarrassed by my rosacea (item #7)

I am frustrated by my rosacea (item #8)

I am annoyed by my rosacea (item #10)

I am bothered by the appearance of my skin (redness, blotchiness) (item #11)

My rosacea makes me feel self-conscious (item #12)

I am bothered by persistence/reoccurrence of my rosacea (item #14)

I think about my rosacea (item #20)

Each individual item should be scored as follows: 1=Never, 2=Rarely, 3=Sometimes, 4=Often, and 5=All the time. Missing data values will not be used. If a subscale has items with missing results, the subscore and the total will not be calculated.

